#### **V.6. Patient Satisfaction Surveys (Specific Aim 4)**

We plan to collect quantitative data about patient satisfaction with the navigators in Lung screening patient navigation (PN) program. We will ask patients who have been randomized to PN early intervention arm to complete two validated surveys: "Satisfaction with Interpersonal Relationships with Navigator (PSN-I)" and "Satisfaction with Logistical Aspects of Navigation (PSN-L)". We will also ask both the PN early intervention group and the delayed intervention group to complete the Short-form Patient Satisfaction Questionnaire (PSQ-18). These surveys will provide information about patient satisfaction with the PN program and information about the impact of the PN program on overall patient satisfaction with medical care.

Patients will be contacted by telephone and asked to participate if they received PN services as part of the Lung screening PN program and had contact with navigator. Those interested in participation may then complete the surveys over the telephone or they may elect to complete the surveys in person and will be met by an interviewer at their next MGH clinic appointment. Patient interviews will last approximately 20 minutes in duration (see attached surveys and interview guide). Bilingual research assistants or trained interpreters will be available to conduct surveys if patients are not native English speakers. Exclusion and inclusion criteria are the same as Specific Aim 2.

## V.7. Provider Surveys (Specific Aim 5)

Following the completion of the randomized trial of the lung cancer screening PN program in current smokers receiving primary care at MGH CHCs, we plan to survey primary care providers to assess their opinions and experience with the program with a short 8 question survey. The study PI will visit the 5 CHCs at regularly scheduled practice meetings to present the overall results of the randomized trial, and will ask PCPs and NPs from these practices to complete a paper version of the survey at the meeting. For providers who do not attend the meeting, we will send them the survey via interoffice mail or email. The survey will not collect any personal or demographic data. All providers from the participating practices will be eligible to receive the survey.

## VI. BIOSTATISTICAL ANALYSIS

### VI.1 Primary outcomes (intention-to-treat)

Percentage of patients assigned to the intervention and control groups who had at least one chest CT (according to billing and EMR data) during the 1-year study period.

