## **I. SPECIFIC AIMS**

**Specific Aim 1:** To develop a patient navigator (PN) program for lung screening for patients who are current smokers, aged 55-77 years, potentially eligible for lung screening and are receiving care at community health centers (CHCs) affiliated with MGH.

**Specific Aim 2:** To evaluate the effectiveness of the new lung screening PN program in improving screening rates and increasing use of tobacco cessation services in a randomized controlled trial.

**Specific Aim 3:** To demonstrate that equity is maintained in rates of lung screening and in follow up of abnormal chest CT results, comparing eligible smokers from CHCs with eligible smokers from other practices within the MGH primary care network.

**Specific Aim 4:** To collect quantitative data about patient satisfaction with the navigators in the lung screening PN program

**Specific Aim 5:** To explore CHC primary care providers opinions about the lung screening PN program via survey

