The availability and coverage for LDCT screening does not mean that all eligible individuals will be screened. To improve cancer screening and follow-up in vulnerable populations, various strategies have been evaluated, including patient navigation. Implemented in 1990 by Freeman, patient navigation (PN) uses culturally and linguistically tailored outreach workers to explore barriers to cancer care and navigate patients to obtain necessary care. Several studies have shown that patient navigation can significantly improve breast and colon screening rates, follow up after abnormal results and decrease disparities in care. Currently, lung screening with LDCT has not been widely used at Massachusetts General Hospital (MGH). As a result, we have a unique opportunity to investigate how to promote screening in eligible, vulnerable patients and to prevent the creation of disparities in care.

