### **III. SUBJECT SELECTION**

According to internal MGH data from 2012, 1480 patients aged 55-79 years at MGH CHCs were current smokers. Of these patients, 204 had a chest CT scan in the prior 18-months and/or had a diagnosis of lung cancer. Because of new Medicare guidelines we will only include patients that are aged 55-77 years and additionally exclude patients that providers deem ineligible for lung cancer screening. We estimate the total number of patients eligible for our interventions to be around 1200. Our experience in prior PN colorectal cancer screening interventions is that one full-time navigator assigned 400 patients will be able to reach/work with 300 patients over a 9-month period. Since our navigator will also follow-up abnormal CT results, our study will last one year. Eligible patients will be identified, randomized, and an electronic list of patients will be downloaded into an existing TopCare navigator data base. The navigators will use this system to track patients and interventions. Patients randomized to the interventions group will be recruited by navigators during their visits to the health center or over the phone. Since the navigator program is already standard of care at MGH, its expansion to include lung screening is considered part of usual care.

For Specific Aim 5, primary care physicians (PCPs) and nurse practitioners (NPs) from the community health centers with the PN program will be asked to complete a survey following the study period. There are approximately 81 PCPs and NPs who will be asked to complete the survey.

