## **V. STUDY PROCEDURE**

### **V.1. Overview**

We propose to develop, implement, and rigorously evaluate a novel lung screening patient navigator program for patients that currently smoke in five community health centers affiliated with a primary care network of a large academic hospital.

Eligible patients will include those receiving care in community health centers who are 55-77 years old and currently smoking. The intervention trial will be randomized at the patient level. In the intervention group, patients will be contacted by a culturally competent PN who will help them stop smoking and obtain lung screening. The control patients will receive usual care. The primary outcome will assess the percentage of eligible patients in intervention and control groups who had at least one chest CT during the study period. Secondary outcomes will include as-treated primary outcomes among intervention patients contacted by the patient navigator, primary outcomes stratified by language spoken, race, age, and practice site, follow-up of abnormal results, percentage of patients with tobacco treatment, and comparison of lung screening to other practices in the primary care network.

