### VI.2 Secondary outcomes

1. Percentage of patients who had at least one chest CT (according to billing and EMR data) during the 1-year study period, comparing patients contacted by patient navigator in the intervention group ("as treated" analysis) vs. all patients in control group.
2. Percentage of patients in intervention vs. control groups who had at least one lung CT screening stratified by language spoken, race, age (<> 65 years) and practice site. (subgroup analysis)
3. Of patients whose initial chest CT generated a radiologist's recommendation for early interval follow-up, the percentage who received the recommended follow-up of in timely manner. The timeliness of care is defined by radiologist's recommendation plus additional 30 days. For recommended biopsy/PET scan we chose 60 days limit. All radiologists at MGH use Lung-RADS system to recommend the follow up post LDCT. These standardized recommendations include 12, 6 or 3 months follow up or for suspicious malignancy PET CT vs biopsy. There is some variability in reading diagnostic chest CT; however recommendations are similar to Lung-RADS. At the end of one-year trial a blinded research assistant will review the electronic medical records of patients who had a chest CT during study period. The dates of imaging will be confirmed by billing data.
4. Mean time to follow-up of abnormal results, comparing intervention and control groups.
5. Tobacco treatment use: Percentage of patients, comparing intervention and control groups, who during the 1-year study period had any of the following:
  - o referral to MA Quitline as determined by patients' QuitWorks data or referral scanned in EHR
  - o smoking cessation medication prescribed in EHR (nicotine patch, gum, lozenge, inhaler, nasal spray or bupropion, or varenicline) during the study period
  - o referral to in-person counseling from CHC-based tobacco coach –documented in EHR
6. Percentage of patients, comparing intervention and control groups, who have a status of former or nonsmoker entered in coded field of EHR at the visit closest to the date of 1 year follow-up.
7. Percentage of patients in intervention group who are reached by PN and percentage of patients reached who had lung screening (process measures)

## AIM 3

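### The primary outcome counts any chest CT but is described and powered as lung screening, and no defined whole-arm comparison of screening LDCT is prespecified

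*Combined protocol and SAP*

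**What the plan says.** Specific Aim 2 is to evaluate the "effectiveness of the new lung screening PN program in improving screening rates". Section II describes screening as LDCT in people without signs or symptoms of lung cancer, with a written order and a shared decision visit.

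Section VI.1 defines the primary outcome as the percentage in each arm who "had at least one chest CT (according to billing and EMR data) during the 1-year study period". Section V.1 agrees: patients "who had at least one chest CT during the study period". Neither names LDCT, an indication or a procedure code. Section VI.2, item 3, on follow-up of abnormal results, says "There is some variability in reading diagnostic chest CT", so diagnostic scans are among those considered.

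Section VI.3 calls the compared quantity lung screening rates, and section VI.4 states the 5-point hypothesis for lung screening. Neither distinguishes it from chest CT.

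Screening appears in two secondary outcomes:

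- Item 2 is the "Percentage of patients in intervention vs. control groups who had at least one lung CT screening stratified by language spoken" and by race, age and practice site. It is a subgroup analysis only, and section V.1 describes the same stratification as applying to the primary outcomes.
- Item 7 gives the percentage screened among intervention patients whom the navigator reached. It has no control arm.

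**The concern.** The event counted and the event claimed differ. A chest CT done for symptoms meets the responder definition in either arm, although it is not screening as section II describes it. If the plan is followed as written, a chest CT rate will be reported as a screening rate. Both arms' percentages will be too high for that label, and the difference will be diluted by scans that navigation was not meant to change. Nothing in the outcome list corrects this, because the term lung CT screening in item 2 is undefined and may be the primary outcome under another name. If scans are classified only after results by arm are known, any statement about LDCT becomes post hoc.

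**Working it through.** **Inputs.** Intervention arm 400 (V.4, VI.4). Control arm 800 (V.4 table) or 1276 − 400 = 876 (VI.4). Difference 5 points, alpha 0.05, stated power 88% (VI.4). No control rate is given, and sidedness is not stated.

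**1. The plan's own figure.** Two-sided normal approximation:

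power = Φ[(Δ − 1.96·SE0)/SE1], where SE0 = √[p̄(1−p̄)(1/n1 + 1/n2)] and SE1 = √[p1(1−p1)/n1 + p2(1−p2)/n2].

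For 10% versus 5% with 400/800: p̄ = (40 + 40)/1200 = 0.0667, SE0 = 0.01528, SE1 = 0.01686. Power = Φ[(0.05 − 0.02995)/0.01686] = Φ(1.19) = 88.3%. With 400/876 it is 89.2%. The stated 88% therefore fits a control rate of about 5%, but that rate is inferred. At a 10% control rate, power for 5 points is 72.3% (400/876).

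**2. Background rate.** The only related figure is in section III: of 1480 current smokers aged 55-79, "204 had a chest CT scan in the prior 18-months and/or had a diagnosis of lung cancer". That is 204/1480 = 13.8% over 18 months, or 13.8% × 12/18 = 9.2% per year (9.4% under a constant hazard). Section II says "lung screening with LDCT has not been widely used at Massachusetts General Hospital", so few of these scans are likely to have been screening. The figure is only a rough guide. It includes lung cancer diagnoses, covers a wider age range, and describes patients whom section V.4 then excludes. Below, 9.2% is a high illustrative value, with 3% and 5% as lower assumptions.

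**3. Share of intervention-arm events that are not screening.** Assume negligible control screening and an undiluted 5-point gain. Share = b/(b + 5), with b the background percentage:

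- b = 3: 3/8 = 38%
- b = 5: 5/10 = 50%
- b = 9.2: 9.2/14.2 = 65%

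**4. Dilution.** Assume screening of 5% versus 10% and a diagnostic rate b that is equal in both arms and independent of screening. The any-CT rate is 1 − (1 − s)(1 − b), with s the screening rate. Arms are 400/800.

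| b | Control any CT | Intervention any CT | Difference (points) | Power |
|---|---|---|---|---|
| 0 (LDCT alone) | 5.0% | 10.0% | 5.00 | 88% |
| 3% | 7.85% | 12.70% | 4.85 | 76% |
| 5% | 9.75% | 14.50% | 4.75 | 68% |
| 9.2% | 13.74% | 18.28% | 4.54 | 54% |

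In this scenario the intervention-arm events without a screening scan are (12.70 − 10)/12.70 = 21%, (14.50 − 10)/14.50 = 31% and (18.28 − 10)/18.28 = 45%, so the shares in step 3 depend on control screening being negligible. With screening of 1% versus 6%, power is 99% for LDCT alone and 91%, 82% and 63% for any CT.

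**5. Precision.** The 95% half-width is 1.96·SE1 with 400/800. For any CT at 14.2% versus 9.2% it is 4.0 points. For LDCT it is 3.3 points at 10% versus 5%, or 2.4 points at 6% versus 1%. The gain in precision thus depends on the assumed control screening rate.

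**The case against.** Any chest CT is a coherent endpoint. Section V.4 excludes patients with any chest CT in the previous 18 months, so eligibility and outcome use the same event, and Aim 3 uses it too. Billing data can capture it without judgement about indication. This stands, and it is a reason to keep the primary outcome.

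The 88% may also have been calculated with 5% as the any-CT control rate. If so, the planned power is not reduced for that outcome; the hypothesis is then about chest CT completion, and the labelling problem remains.

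Three stronger readings are tempting but unsupported:

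- A reader might infer that the trial cannot report a screening rate. Billing and EMR data are collected, and a blinded assistant reviews the records of patients with a chest CT. The rate is undefined and not prespecified, which is different from unobtainable.
- A reader might infer that symptom-driven scans are credited to the navigator. Randomisation is by patient, so background scans count in both arms and mainly dilute the effect. Bias towards navigation would need navigator contact itself to prompt diagnostic scans. That is possible, since navigators arrange provider visits, but nothing in the documents shows it.
- A reader might infer that most events will not be screening. That holds only at the higher backgrounds with little control screening, and 204/1480 cannot establish such a background in the enrolled patients.

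**Conclusion.** The mismatch is on the face of the documents: the outcome is any chest CT, the conclusion is worded as lung screening, and no defined, unstratified, whole-arm comparison of screening LDCT is listed. The consequences are inflated screening rates in both arms and a diluted difference; a false positive result for navigation is not implied.

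The size depends on a background rate that the documents do not supply. Over 3% to 9.2%, non-screening scans would be about 38% to 65% of intervention-arm events if control screening is negligible. Power for any chest CT would be about 76% down to 54%, against 88% for LDCT alone, if screening is 5% versus 10% and diagnostic scans are equal in the two arms and independent of screening. These are illustrations, not bounds. The point should be addressed before results by arm are seen; it does not require replacing the primary outcome.

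**What to change.** - Keep any chest CT as the primary outcome, and describe it in VI.1, VI.3 and VI.4 as chest CT completion. In VI.4, state the control rate behind the 88% and the outcome to which it refers.
- Add a prespecified intention-to-treat secondary outcome: the percentage of all randomised patients in each arm with at least one screening LDCT during the study year. Identify these scans by LDCT billing code or by a screening indication in the order or report, classified blind to arm within the record review already planned.
- Report the primary outcome split into screening and diagnostic CT by arm. This would also show whether diagnostic scans differ between arms.
- Base any statement about lung screening rates on the LDCT outcome, and report it as a secondary result. If the two outcomes disagree, report both under their own names.
- Use the same definition in item 2 and item 7 of VI.2.

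The cost is a change of SAP wording, one more extracted field, one more secondary comparison and a lower headline percentage.

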### VI.2 Secondary outcomes

1. Percentage of patients who had at least one chest CT (according to billing and EMR data) during the 1-year study period, comparing patients contacted by patient navigator in the intervention group ("as treated" analysis) vs. all patients in control group.
2. Percentage of patients in intervention vs. control groups who had at least one lung CT screening stratified by language spoken, race, age (<> 65 years) and practice site. (subgroup analysis)
3. Of patients whose initial chest CT generated a radiologist's recommendation for early interval follow-up, the percentage who received the recommended follow-up of in timely manner. The timeliness of care is defined by radiologist's recommendation plus additional 30 days. For recommended biopsy/PET scan we chose 60 days limit. All radiologists at MGH use Lung-RADS system to recommend the follow up post LDCT. These standardized recommendations include 12, 6 or 3 months follow up or for suspicious malignancy PET CT vs biopsy. There is some variability in reading diagnostic chest CT; however recommendations are similar to Lung-RADS. At the end of one-year trial a blinded research assistant will review the electronic medical records of patients who had a chest CT during study period. The dates of imaging will be confirmed by billing data.
4. Mean time to follow-up of abnormal results, comparing intervention and control groups.
5. Tobacco treatment use: Percentage of patients, comparing intervention and control groups, who during the 1-year study period had any of the following:
  - o referral to MA Quitline as determined by patients' QuitWorks data or referral scanned in EHR
  - o smoking cessation medication prescribed in EHR (nicotine patch, gum, lozenge, inhaler, nasal spray or bupropion, or varenicline) during the study period
  - o referral to in-person counseling from CHC-based tobacco coach –documented in EHR
6. Percentage of patients, comparing intervention and control groups, who have a status of former or nonsmoker entered in coded field of EHR at the visit closest to the date of 1 year follow-up.
7. Percentage of patients in intervention group who are reached by PN and percentage of patients reached who had lung screening (process measures)

## AIM 3

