## V.2. Time Line

As depicted in **Table 1**, the work planned for **Specific Aim 1** is occurring during Study Year 1. Development of the program, hiring and training navigators, as well as organizational aspects that are necessary to permit the timely implementation and evaluation of the intervention (**Specific Aim 2**) will occur over the course of Year 2 with completion in early Year 3. The remainder of Year 3 will be devoted to outcomes evaluation, (**Specific aim 3**) analysis, and dissemination.

Task	0-4	5-8	9-12	13-16	17-20	21-24	25-28	29-32	33-36
Specific Aim 1									
Develop smokers registry									
Software development for PN									
Develop curriculum and procedure manual for PN									
Present the program at CHC PCP meetings									
Develop educational materials for patients									
Navigator training									
Specific Aim 2 and 3									
Randomization									
Baseline evaluation									
Intervention									
Outcome evaluation (at 1 year)									
Analysis & manuscript writing									
Dissemination									
Note: Lighter shaded boxes denote option for additional time if needed.									

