### **VI.3. Analytic Methods**

#### **AIM 2:**

We will examine differences in lung screening rates using chi-square tests.

The comparisons include (1) between intervention and control groups (intention-to-treat analysis), and (2) between patients contacted and not contacted by patient navigators (“as-treated” analysis).

An exploratory subgroup analysis will compare lung screening rates between intervention and control groups stratified by language spoken, race, age (<> 65 years), practice site and other factors.

Furthermore, we will use logistic regression models to examine predictors of lung screening, including patient, provider, and practice characteristics.

In addition to comparing the percentage that completed recommended test in a timely manner between intervention and control group using a chi-square test, we will use survival analysis techniques to compare time to completion between intervention and control groups.

We will also use chi-square tests to compare the percentage with referral to MA Quitline, prescription to smoking cessation medications, referral to in person counseling from CHC tobacco coach, and documented smoking status in EHR between intervention and control groups.

For the intervention group, we will document process measures (percentage reached by PN and percentage agreed to have lung screening test within) and present with 95%CI's.

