### **VI.4. Sample Size Calculations**

We hypothesize that the navigator program will increase lung screening in the intervention group by at least 5%. With a total sample size of 1276 smokers, 400 randomized to the intervention group, and an alpha level of 0.05, we will have 88% power to detect a 5% difference. From our prior experience, a full time navigator with the assistance of two part-time interpreters/navigators can reach about 400 patients over nine months. Since our intervention includes follow-up of abnormal results, our study will last 1-year.

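### The timely-follow-up percentage (VI.2 item 3) includes patients whose follow-up window is still open when the study year ends

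*Combined protocol and SAP*

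**What the plan says.** VI.2 item 3 takes patients whose initial chest CT led to a recommendation for early interval follow-up and reports "the percentage who received the recommended follow-up of in timely manner". The window is the radiologist's recommended interval plus 30 days; the exception is "For recommended biopsy/PET scan we chose 60 days limit". The intervals listed are 12, 6 or 3 months. On ascertainment: "At the end of one-year trial a blinded research assistant will review the electronic medical records of patients who had a chest CT" during the study period. No latest date for an eligible initial CT is given.

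Item 4 is "Mean time to follow-up of abnormal results, comparing intervention and control groups".

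VI.3 (Aim 2) covers both items in one sentence. It begins "In addition to comparing the percentage that completed recommended test in a timely manner between intervention and control group using a chi-square test" and continues "we will use survival analysis techniques to compare time to completion between intervention and control groups". No time origin or censoring date is given.

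On the end of data, VI.4 says "Since our intervention includes follow-up of abnormal results, our study will last 1-year", and Table 1 places outcome evaluation at 1 year. V.2 says "The remainder of Year 3 will be devoted to outcomes evaluation". V.4 spreads the navigator's first letters and calls over the first six months and offers controls navigation, including help with abnormal results, once the year is over.

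**The concern.** A yes/no outcome with a fixed window can be scored only when the window has closed or the event has already happened. Item 3 admits CTs up to the last day of the year, and its records are reviewed when that year ends. A patient scanned in month 11 and asked to return in six months cannot have met or missed the target by then. The chi-square test still needs a yes or a no, and under the stated denominator such a patient falls among those without timely follow-up.

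Two things are at stake. The reported percentage would be too low in both arms. The comparison could also shift if the arms differ in when CTs occur, which is plausible because only the intervention arm has outreach staged over six months. Item 4 has a smaller, related problem: a mean time cannot be computed for patients not yet followed up.

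**Working it through.** The plan gives no figure for item 3 or item 4, so there is none to reproduce.

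**Inputs from the plan.** Windows: interval + 30 days, or 60 days for PET/biopsy (VI.2). Study year: 365 days. Letters over months 0-6 (V.4).

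**Assumptions.** 3 months = 91 days and 6 months = 183 days. A 12-month recall is routine, not early; if it counted as early, its 395-day window could never close within the year. CTs are uniform over the year unless stated otherwise.

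**Step 1: which windows are open at one year.** Last CT day with a closed window = 365 − window. Open share = window / 365.

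| Recommendation | Window (days) | Last closed CT day | Open share | Remaining |
|---|---|---|---|---|
| 3 months | 91 + 30 = 121 | 244 | 121/365 = 33% | 67% |
| 6 months | 183 + 30 = 213 | 152 | 213/365 = 58% | 42% |
| PET/biopsy | 60 | 305 | 60/365 = 16% | 84% |

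If data ran 60 days past the year, the open shares would be 61/365 = 17%, 153/365 = 42% and 0. At 120 days past they would be 0.3%, 25% and 0. All windows are closed only 213 days after the year ends.

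**Step 2: effect on the percentage.** Assume 80% are truly timely, with follow-up uniform over the 30 days after the due date (over 60 days for PET/biopsy). Observed rate = 0.80 × (1 − mean follow-up time / 365):
- 3 months: 0.80 × (1 − 106/365) = 57%
- 6 months: 0.80 × (1 − 198/365) = 37%
- PET/biopsy: 0.80 × (1 − 30/365) = 73%

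**Step 3: effect on the comparison.** If CT timing is the same in both arms, the expected difference from this source is zero. To see what unequal timing could do, control CTs were kept uniform and half of intervention CTs were assumed to follow a navigator letter, with letters uniform over months 0-6. True rates were 80% in both arms. Intervention minus control by simulation, in the order 3-month, 6-month, PET/biopsy:
- CT 1-3 months after the letter: +11, +5, +3 points
- CT 3-6 months after the letter: −2, −11, +2 points

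If letters are instead weighted towards the start of the six months, the 3-6 month lag gives about +6 (3-month) and −6 (6-month). The sign is not predictable.

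**Step 4: precision.** VI.4 states 88% power for a 5-point difference with 400 intervention patients out of 1276, so 876 controls. It gives no control rate. A two-sided pooled test reaches 88% at a control rate of about 5.35%. That implies about 400 × 10.35% = 41 and 876 × 5.35% = 47 patients with a CT. If 20% of these need early follow-up (assumption), there are about 8.3 and 9.4 patients. The 95% half-width of the difference is then 1.96 × √(0.16 × (1/8.3 + 1/9.4)) = 37 points. It is 53 points if 10% need early follow-up and 31 if 30% do.

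**Step 5: does restriction work?** Keeping only patients whose full window closes by day 365 returns 80% within each interval. Dropping only the open windows without follow-up does not: for 3 months it gives 0.568 / (0.668 + 0.568 − 0.80 × 0.668) = 81%, because early successes are kept and their counterparts removed. Pooling closed windows over intervals also changes the mix. With assumed true rates of 80%, 60% and 95% (3-month, 6-month, PET/biopsy) in equal shares, the truth is 78.3%. The pooled closed-window figure is 82.2% in controls and 84.4% in the intervention arm at the 3-6 month lag.

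**The case against.** The strongest objection is that the plan fixes when charts are reviewed, not the last date on which follow-up counts, and never instructs anyone to score open windows as failures. V.2 leaves much of Year 3 for evaluation, and Table 1's one-year label may name an outcome time point rather than a data stop; its shading cannot be read in the available text. This stands in part. The figures in Steps 1 and 2 are conditional on data ending at one year. But no section states a later date or another scoring rule, and the stated denominator, review time and chi-square test lead to that scoring by default. Reading charts later is not a clean escape either, because controls may then be navigated.

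A reader might infer that the plan has no way to handle unfinished follow-up. It does: the survival analysis in VI.3 can censor it. It is planned alongside the percentage rather than in its place, so item 3 remains exposed. For item 4, what remains is a wording mismatch and an unstated origin and censoring date.

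A reader might also infer that the comparison is biased for or against navigation. The documents do not support that. They give no CT timing by arm, the Step 3 figures rest on several assumptions, their sign changes with the lag, and all are smaller than the sampling error in Step 4.

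**Conclusion.** The concern holds for item 3. With data ending at one year, about a third of 3-month windows, more than half of 6-month windows and a sixth of PET/biopsy windows are open under uniform CT timing. Counting those without follow-up as not timely would turn an assumed 80% into 57%, 37% and 73%. The understatement in both arms is the firmer consequence. Bias between arms is possible in either direction and is zero in expectation if CT timing is equal.

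The reach is limited. The primary outcome is untouched, and items 3 and 4 are secondary outcomes likely to rest on a handful of patients per arm. With so few, fixing the rule before the data are seen matters, because rescoring two or three patients would change the result. The change should be made, but the trial does not depend on it.

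**What to change.** In VI.2 item 3, state one data cut-off, at one year, for both arms. A later cut-off would mix navigated follow-up into the control arm. Censoring only controls at one year while reading intervention charts for longer would give the arms unequal follow-up.

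Then choose one of two analyses:
- restrict the percentage to patients whose full window closes by the cut-off, whether or not follow-up has already occurred; or
- replace it with Kaplan-Meier completion by the end of the window, timed from the initial CT and censored at the cut-off.

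Report counts by recommended interval with either choice, since pooling changes the mix (Step 5). An interval-stratified test is optional if numbers allow; with so few patients some strata may be empty in one arm.

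In item 4, replace the mean with the survival analysis already planned in VI.3, using the same origin and censoring date.

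The cost is SAP wording, with no chart review beyond the one-year cut-off. The downside is fewer patients in the restricted percentage: about 67%, 42% and 84% of the 3-month, 6-month and PET/biopsy groups remain under uniform timing.
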